4.1 Objectives

[figure not shown]
1. Determine risk factors for neonatal early-onset sepsis in Kampala, Uganda
2. Use machine learning techniques to create a risk stratification model for early-onset sepsis in Uganda
3. Explore relationship between culture-positive sepsis and clinical diagnostic features in Uganda using machine learning techniques, including association between level of training of clinician documented diagnosis and blood culture result
4. Validate the model from Uganda externally using an independent dataset from a neonatal population in Harare, Zimbabwe

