4.2 Outcome

- Primary outcome for Phase 1: Positive blood culture amongst neonatal participants
- Primary outcome for Phase 3: Clinician (specialist neonatal or paediatric doctor) diagnosis of sepsis amongst neonatal participants as documented in clinical notes or discharge letter
- Clinical features of neonatal sepsis as listed in GAIA neonatal infections case definition
- Admission to neonatal unit
- Readmission to hospital in first 28 days amongst neonatal participants
- Death before 28 days of age
- Sensitivity, specificity, positive and negative predictive value of risk stratification model for participants in Kampala and Harare

Using machine learning to model early-onset neonatal sepsis risk in Uganda (NeoRisk)

5 STUDY DESIGN and METHODS of DATA COLLECTION AND DATA ANALYSIS

There will be three main phases to this study, which is an observational cohort study.

Using machine learning to model early-onset neonatal sepsis risk in Uganda (NeoRisk)

Phase 1 will take place at Kawempe Hospital in Kampala, Uganda. Participants will be recruited from labour wards by study staff, and interim analysis will be completed after recruitment of 10% of the total sample. See section 7.3 for further details.

Data will be collected via an online CRF, including the factors listed in the table in Section 3.

Additionally:

- All neonates within the study will have a **neonatal venous blood sample** taken for culture by designated study staff
 - This must be taken before administration of antibiotics or within 48 hours of birth, whichever is sooner, and regardless of whether the neonate is being investigated and treated for sepsis.
- **Postnatal information** will be collected via telephone at 1 month including maternal and infant outcome, hospital readmission or clinical illness, and vaccines given

All data will be checked for quality control by a member of the study team.

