A blood culture will be taken from all neonatal participants at birth, prior to starting antibiotic treatment wherever safe to do so. The volume of blood taken for culture must be 1-2ml and will be verified by weighing blood culture bottles. Training will be provided to paediatric and study teams on blood culture sampling methods, including adequate cleaning of the skin prior to sampling. Feedback on sample volumes and contamination rates (see section 7.3 for definition) will be fed back to paediatric consultants, and additional staff training offered. Where sample is remaining after 3ml is added to the culture bottle, the excess will be retained as a blood spot sample for use in future ethically approved research, where the participant has consented to this.

The results of the microbiological tests will be communicated to the participant's clinical team in real time – see section 7.3.4 for further details. Clinician diagnosis of sepsis will be recorded where a clinician of registrar level or above has recorded a diagnosis of sepsis within 48 hours of birth. To reduce the subjectivity of this measure, GAIA level of certainty for a diagnosis of sepsis will also be assessed (35) and the level of diagnostic certainty recorded (1-5, as per GAIA criteria). Medical records are recorded on paper at Kawempe Hospital, before being coded into an electronic medical record by data clerks. PDF scans of medical records will be available where detailed review is required.

All participant data will be collected by trained study staff, and recorded into an online CRF hosted on REDCap, a secure web application. No patient identifiable data will be stored on the main REDCap database. See section 8.6 for further details of data management plans.

The postnatal information will be completed via a telephone call at 28 days post-delivery, made by study staff. Participants' contact number, a contact number for their partner, and a contact number for a second friend or family member will be taken at recruitment to minimise loss to follow up due to changes to mobile telephone number. Participant identity will be confirmed using three factors (date of birth, full name, address/village). The following information will be collected:

- Health status of mother and baby
- Any visits to medical care for the neonate
 - If attended or admitted to Kawempe hospitals, these electronic medical records will be reviewed by study staff

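### Site and sepsis reference standard change together between Kampala and Harare, and no like-for-like Kampala accuracy figure is planned, so a difference in accuracy would mix change of label with transport

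*Combined protocol and SAP*

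**What the plan says.** Section 4.2 gives two primary outcomes: "Primary outcome for Phase 1: Positive blood culture amongst neonatal participants" and "Primary outcome for Phase 3: Clinician (specialist neonatal or paediatric doctor) diagnosis of sepsis". The second may be taken from the notes or the discharge letter, and 4.2 gives no time window for it. The last outcome in the same list is "Sensitivity, specificity, positive and negative predictive value of risk stratification model for participants in Kampala and Harare", with no reference standard named for either site.

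In Kampala every infant is cultured (sections 2 and 5). Section 5 also has staff record a clinician diagnosis where "a clinician of registrar level or above has recorded a diagnosis of sepsis within 48 hours of birth", and adds that "GAIA level of certainty for a diagnosis of sepsis will also be assessed". Culture results go to the infant's "clinical team in real time".

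For Harare, section 5 describes the outcome as a senior clinician's diagnosis within 48 hours of delivery. Cultures are taken only when available, and only in infants at risk or with signs. The stated reason is unreliable supply of culture bottles and laboratory analysis. Section 5 also says the data collected will match Phase 1.

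Objective 4 (section 4.1) is to "Validate the model from Uganda externally using an independent dataset". Section 5 says Phase 3 will show the model's accuracy in a second population and explore generalisability.

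The machine learning part of the data analysis in section 5 does not name the training label. Sections 2, 4.2 and 7.2.1 point to culture. The aims in the Study Summary accept either culture or a senior clinician's diagnosis, and section 3 says methods other than culture must be considered for the model to be accurate.

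**The concern.** External validation asks whether a model performs in new patients as it did in the old ones. If the model is judged by culture in Kampala and by clinicians in Harare, two things change at once.

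A lower Harare figure could mean that the model does not travel, or only that clinicians label many culture-negative infants as septic. A similar or higher figure could mean that it travels well. It could also arise because clinical signs are both candidate predictors (table in section 3) and part of what the clinician judges.

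The protocol itself treats the label as important. Section 1 suggests that earlier low-resource models may have performed modestly because they rested partly on clinician-defined sepsis, and section 3 calls an individual clinician's diagnosis subjective. The label that would help separate these readings is already being collected in Kampala. At stake is how Objective 4 can be interpreted.

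**Working it through.** The plan gives no figure for the Kampala-Harare comparison, so there is none to reproduce. The check is mainly a reading of the text, followed by two short calculations.

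**1. Does any planned use of the Kampala clinician diagnosis score the risk model?**

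| Place | Planned use | Scores the model? |
|---|---|---|
| Section 3, diagnosis of neonatal sepsis | Named as a secondary outcome | No analysis attached |
| Section 4.1, Objective 3 | "Explore relationship between culture-positive sepsis and clinical diagnostic features in Uganda using machine learning techniques", including the clinician's level of training | No |
| Section 5, pilot after 160 participants | Association of risk factors with clinical or culture-positive sepsis | No |
| Section 5, logistic regression | Risk factors for clinical and microbiological diagnoses | No; a cross-check on the principal model |
| Section 4.2, last outcome | Accuracy at both sites | Reference standard not named: permitted, not planned |
| Section 5, Phase 3 analysis | Sensitivity, specificity, predictive values, AUC | Harare data only |

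Followed as written, the plan yields no Kampala figure on the Harare label.

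**2. Can size or direction be read from the documents?** Suppose the model keeps the 90% sensitivity for culture-positive sepsis used for planning in 7.2.1, with no loss in transport. Let f be the culture-positive share of clinician-diagnosed cases and r the share of culture-negative cases that the model flags. Then

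apparent sensitivity = 0.9f + (1 − f)r.

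Low f: section 3 cites up to 16 culture-negative cases per culture-positive case, so f = 1/17 = 0.059. High f: 7.2.1 gives up to 5% culture-positive (Kampala) and 16% clinical sepsis (Harare planning rate), so f = 0.05/0.16 = 0.3125 if every culture-positive infant is also diagnosed by a clinician. The documents give no r, so the values below are assumed.

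| Assumed r | f = 0.059 | f = 0.3125 |
|---|---|---|
| 0.20 | 0.241 | 0.419 |
| 0.50 | 0.524 | 0.625 |
| 0.95 | 0.947 | 0.934 |

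The assumed r drives the result, and the two values of f mix populations. The table shows that the planned figures cannot separate label from transport. It is not an effect size, and it assumes training on culture.

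**3. Is a Kampala comparator precise enough?** The reserve is 0.20 × 1600 = 320 infants, and at 5% that gives 320 × 0.05 = 16 culture-positives. If 14 of 16 are detected, the Wilson 95% interval is 64% to 97%. In all 1600 there are about 80; if 72 are detected, it is 81% to 95%.

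No Kampala rate of clinician diagnosis is given. At an assumed 5% to 16%, the Wilson half-widths near 50% sensitivity are:

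- Reserve: 16 to 51 cases, about ±22 to ±13 points.
- All 1600: 80 to 256 cases, about ±11 to ±6 points.

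Intervals for all 1600 treat cross-validated or bootstrap-corrected estimates as simple proportions, so they are approximate.

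**The case against.** The switch is open and justified: complete cultures cannot be obtained in Harare. Section 5 speaks only of exploring generalisability, and no section plans a formal Kampala-Harare difference or attributes one to transport. The accuracy outcome in 4.2 names no reference standard, so it already allows clinician-label scoring in Kampala. Objective 3, the logistic regression and the GAIA levels are partial bridges. The terms for clinician grade (registrar or above, senior, specialist) are not defined against each other and may overlap.

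Much of this stands. The choice of outcome in Harare is not contested, and a real difference in clinician grade is not shown. But justifying a label does not supply a comparator, and none of the bridges scores the model.

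Three stronger readings are tempting, and the documents do not support them.

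- A reader might infer that the model is certainly trained on culture. The Study Summary and section 3 leave that open.
- A reader might infer a predicted fall in Harare sensitivity. That rests on assumed flag rates and mixed denominators.
- A reader might infer that feedback of culture results makes the Kampala clinician label unusable. Processing within 12 hours and 36 hours of incubation (7.3.4) put a final negative about 36 to 48 hours after collection. That falls inside a 48-hour window from birth only if sampling is close to birth, and section 5 also allows sampling up to 48 hours. Early positives could still influence the diagnosis.

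**Conclusion.** The point holds. Site and reference standard change together, and the plan contains no accuracy figure on a common label, so a Kampala-Harare difference cannot be read as transport alone. The documents fix neither the size nor the direction of the label effect, and it would be smaller under the culture-or-clinician label.

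Confidence is high that no scoring against the Kampala clinician diagnosis is planned. It is lower for any numerical consequence, which depends on an inferred training label and assumed flag rates.

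It would go too far to say that a comparator would isolate transport. Clinician definitions may still differ. Recruitment source may differ too: section 5 has labour wards in Kampala but antenatal clinics and labour wards in Harare, while 7.3.1 is broader. Kampala clinicians also see culture results. The comparator narrows the ambiguity at little cost and should be added before Phase 3.

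**What to change.** 1. State the training label in the data analysis part of section 5 and align the Study Summary aims with it.
2. State the reference standard for each site in the last outcome of section 4.2.
3. Before Phase 3, lock the model and threshold. Report Kampala accuracy against both culture and the recorded clinician diagnosis, and against GAIA level if it is captured at both sites. Use the clinician-label figures as the comparator for Harare. Because the 20% reserve is imprecise, cross-validated or bootstrap-corrected estimates may be reported alongside it; section 5 already says bootstrapping will be considered.
4. Describe the Harare result as performance against clinician diagnosis. Reconcile the clinician grade, source document and time window between section 4.2 and the Phase 1 and Phase 3 text of section 5.

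The cost is a second set of Kampala accuracy figures on labels already collected, some resampling if it is used, and wording. No extra participants or samples are needed.

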1 BACKGROUND

Sepsis is a leading cause of neonatal mortality worldwide(1), affecting 39.3 per 1000 live births in low- and middle-income countries(2). Mortality from early-onset sepsis can be reduced with prompt, correct treatment with antibiotics(3); therefore, identifying those at risk early is crucial. The sepsis rate in Uganda is high, with an incidence of 68 per 1000 live births, and is highest in hospital facilities(4).

Antibiotics are recommended for neonates with specific risk factors for sepsis, and those with signs of illness, including poor feeding and drowsiness(5). However, many low-resource settings diverge from the World Health Organization (WHO)'s recommended regimens, often due to antimicrobial resistance (5–7) or drug availability(8). Ideally, antibiotics should be given within an hour of birth in cases of suspected early-onset sepsis, which accounts for almost ¾ of sepsis cases in Uganda(4,9).

Additionally, risks of antimicrobial resistance are increasing. Neonates with sepsis in low- and middle-income countries show significant rates of resistance to the extent that the majority of proven infections are resistant to first and second line WHO-recommended antibiotics(10,11). Mortality from sepsis is double with resistant versus sensitive organisms(12). Previous studies in Kampala have shown high rates of resistance to first-line antibiotics(13). Prolonged antibiotic therapy without proven infection is associated with morbidity and mortality in preterm infants, and may affect normal flora and immunity(14,15). Therefore, antimicrobial stewardship is vital for low-resource settings. Accurate, early identification of at-risk neonates allows the benefits of early treatment whilst minimising the harms of overtreatment, and unnecessary admission.

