The 'gold standard' for diagnosis of neonatal sepsis is widely considered to be a microbiological culture of neonatal blood(30), using at least a 1 ml sample(31). However, the proportion of neonatal patients with clinical signs of sepsis whose blood cultures are returned as negative can be significant, with studies reporting between 6 and 16 cases of 'culture-negative sepsis' for every culture-positive case(14). Therefore, although the use of blood culture is the gold standard, other diagnostic methods must be considered in order to capture all cases of neonatal sepsis and subsequently develop an accurate statistical model.

Various proxy biochemical and haematological markers of sepsis are commonly measured and used in clinical practice in high-resource settings, including C-reactive protein, procalcitonin, and full blood counts. These markers are all useful in making a diagnosis of sepsis and monitoring response to treatment, but none have sufficiently high sensitivity or specificity to be used in isolation(30). Additionally, in low-resource settings (including those settings in which this study will take place), access to consumables and laboratory facilities to measure these markers is unreliable. For this study, the use of additional biochemical and haematological markers has therefore been deemed to have limited usefulness in contributing to the statistical model, and so will not be used.

Clinical diagnosis of sepsis is challenging due to the nonspecific signs exhibited by neonates(32) and the lack of a universal definition of clinical sepsis(33). Signs of sepsis are also present in neonates without infection who are transitioning to extra-uterine life, or suffering from other conditions(32,34). However, given the near-universal availability of clinical diagnosis and the limitations of blood cultures to identify all cases of sepsis, we feel it is important to include clinical diagnosis of sepsis as a secondary outcome. Given the subjective nature of an individual clinician's diagnosis, we will also include established criteria for the diagnosis of sepsis that also assess the level of confidence in the clinical diagnosis, to reflect the spectrum of diagnostic certainty. We will therefore use the GAIA neonatal infection case definition criteria to assess cases, which are intended for international use(35,36).

Using machine learning to model early-onset neonatal sepsis risk in Uganda (NeoRisk)

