7.3.3 Data collection tool

Case Report Forms will be designed by the CI. All CRFs will be electronic. The CI will provide logins to relevant and trained site level members of the research team.

It is the Investigator's responsibility to ensure the accuracy of all data entered and recorded in the CRFs. The Staff Delegation of Responsibilities Log should identify all trial personnel responsible for data collection, entry, handling and managing the database.

Prospective patient-level data will be collected from electronic health records (and participant interviews where needed) into an online data entry system (REDCap). This is a secure web application for building and managing online surveys and databases which supports online and offline data capture. This data entry system has been chosen as it will improve the consistency of the data, and allows them to be immediately available in an

Using machine learning to model early-onset neonatal sepsis risk in Uganda (NeoRisk)

analysable format. The data are also stored securely without being stored on an individual hard drive, ensuring their safety and long-term access without need for physical backup.

These data will be anonymised, and will include the parameters outlined in section 5.

Microbiological samples will be taken from the baby, which will be processed locally for blood culture. Gram stain, organism and resistance profile will be inputted to REDCap.

Each data entry form will include the username of the member of study staff who filled out the form, and the date and time it was filled out. Each form will also include a field to input the date, time, and name of the person marking the form as 'complete'. The data entry forms will be tested by members of study staff before being put into production. Data will be reviewed monthly to ensure that data quality is sufficiently high.

Quality control mechanism

Once the study has begun, trained members of study staff will be given their own logins to REDCap to input data. Study staff will also be able to contact the research team to resolve any queries about how or where to input data. Data will either be collected directly from research participants or from their electronic hospital records, but will be inputted directly into REDCap. Data will be reviewed by two study staff members to check for data completeness with reference to scanned medical records.

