7.3.4 Biological Sample Handling

Blood samples will be taken from each neonate for culture (1-2ml) into BACTEC blood culture bottles and stored at room temperature until arrival at the laboratory. Sample volume will be verified by weight, and samples will be labelled with the neonate's ID.

Samples will be processed at Makerere Microbiology Laboratories (College of American Pathologists accredited) within 12 hours of collection(43). Samples will be incubated for 36 hours. Any presumptive positive culture will be plated onto selective agar and identified by biochemical tests. Couriers will collect samples from study sites and transport them to the Medical and Molecular Laboratories (MML) at Makerere University; coverage is available at weekends and some evenings by request from study staff, so a courier will be arranged if a sample is taken more than 12 hours before the next scheduled courier collection.

Sample results will be classified and handled as follows:

- Positive result: known potential pathogenic bacteria

Using machine learning to model early-onset neonatal sepsis risk in Uganda (NeoRisk)

- Pathogens included as per GAIA neonatal infection outcome list of 'recognised pathogens'(35)
- Study staff will notify clinical team and participant's parents by telephone; written notification also to be provided from laboratory (either via electronic system or hard copy) as per routine care
- Contaminant: growth of species considered 'non pathogenic' by GAIA list
 - Review clinical notes to determine presence of risk factors for invasive disease as a result of a normally commensal/contaminant organism (e.g. indwelling venous catheters causing risk of coagulase negative staphylococcal sepsis)
 - If no risk factors, written notification provided to clinical team from laboratory as above
 - If presence of risk factors or uncertainty, study team to additionally contact clinical team via telephone to notify
- Negative result: no growth
 - Written notification provided to clinical team from laboratory as above

Specific written consent will be taken from participants to store any leftover samples for use in future ethically approved research.

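### Section 5 gives two different rules on whether the Phase 1 culture must precede antibiotics, and a no-growth culture taken after antibiotics is by default a non-case

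*Combined protocol and SAP*

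**What the plan says.** - **Outcome.** Section 4.2: "Primary outcome for Phase 1: Positive blood culture amongst neonatal participants". Section 5 uses the Phase 1 data to train the model.
- **Timing, first statement.** Section 5, in the bullet on the venous sample: "This must be taken before administration of antibiotics or within 48 hours of birth, whichever is sooner". It applies whether or not the infant is under investigation or treatment.
- **Timing, second statement.** Section 5, a little further on: "A blood culture will be taken from all neonatal participants at birth, prior to starting antibiotic treatment wherever safe to do so".
- **Classification.** Section 7.3.4 sorts results into positive, contaminant and "Negative result: no growth". A contaminant without obvious significance prompts a review of the notes. A no-growth result prompts only written notification.
- **Data entry.** Section 7.3.3: "Gram stain, organism and resistance profile will be inputted to REDCap". That sentence does not mention timing relative to antibiotics.
- **Who is treated early.** Section 1 recommends antibiotics for infants with particular risk factors as well as those who look ill, and says that ideally "antibiotics should be given within an hour of birth in cases of suspected early-onset sepsis".
- **Analysis and pilot.** The data analysis text in Section 5 has no rule for cultures drawn after antibiotics. The review after 160 participants checks culture volume but does not list culture timing.
- **Other diagnoses.** Section 3: "we feel it is important to include clinical diagnosis of sepsis as a secondary outcome". Section 5 records a sepsis diagnosis by a clinician of at least registrar level within 48 hours of birth, and the GAIA certainty level.

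**The concern.** Both timing statements aim to keep antibiotics from coming before the culture, so the plan itself treats prior antibiotics as a threat to the result. Yet where that aim is not met, nothing says what the result means. A no-growth culture after a first dose is weaker evidence of no infection than one taken before it, but both receive the same label.

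The error need not be random. The risk factors and clinical signs that prompt early treatment in Section 1 are also among the candidate predictors in Section 3. If treatment suppresses growth, the predictors help cause the missing label. Associations between those predictors and culture-positive sepsis could then be understated, and some true cases with high-risk profiles could enter the training data as non-cases. Section 1 asks for sensitivity to be prioritised over specificity, and missed cases in this group work against that.

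There is also a compliance question. Section 8.5 requires deviations to be documented and reported at once. Whether a culture after a first dose is a deviation depends on which sentence of Section 5 is read.

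**Working it through.** **1. The two timing statements side by side**

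| | Bullet in Section 5 | Later paragraph in Section 5 |
|---|---|---|
| Infant not given antibiotics | any time up to 48 h | at birth |
| Infant given antibiotics | before the first dose, mandatory | before the first dose where safe |
| Culture after a first dose | out of protocol | allowed where culture first was unsafe |

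**2. One infant followed through the plan.** Antibiotics are started first because sampling was judged unsafe, and the later culture does not grow. Section 7.3.4 offers positive, contaminant or negative. The infant is negative, hence not a positive culture under Section 4.2, hence a non-case. If the culture grows a recognised pathogen, the infant is still a case, so only the no-growth results are in doubt.

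**3. The plan's own figures.** Section 7.2.1 gives 1460 participants for 90% sensitivity and a 5% rate, and plans 1600. Expected culture-positive infants: 1460 × 0.05 = 73 and 1600 × 0.05 = 80. With the Buderer formula, N = 1.96² × Se × (1 − Se) / d² / prevalence, the half-width d is not stated, so 1460 cannot be reproduced from stated inputs alone. Solving for d gives 1.96 × √(0.09/73) = 6.9 points; with 80 cases it is 6.6 points. The 20% held out for testing would contain 0.2 × 80 = 16 cases. The 5% is given as an upper value, so 80 is towards the high end.

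**4. Cases lost. Assumptions, not in the documents:** 80 infants would be culture-positive if all were sampled before antibiotics; a share f of them is sampled after antibiotics; a share s of those cultures then fails to grow. Loss = 80 × f × s.

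| f | s | lost | observed | half-width at 90% sensitivity | cases in 20% hold-out |
|---|---|---|---|---|---|
| 5% | 25% | 1 | 79 | 6.6 points | 15.8 |
| 10% | 50% | 4 | 76 | 6.7 points | 15.2 |
| 20% | 50% | 8 | 72 | 6.9 points | 14.4 |
| 50% | 75% | 30 | 50 | 8.3 points | 10.0 |

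Observed cases fall below 73 once f × s exceeds 7/80 = 8.75%.

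**5. Effect on an association. Assumptions:** 80 cases and 1520 non-cases; a risk factor in 20% of non-cases (304 exposed, 1216 unexposed); 40 exposed and 40 unexposed cases, so the true odds ratio is (40/40)/(304/1216) = 4.0. Lost cases are relabelled as non-cases.

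- 5 lost, all exposed: (35/40)/(309/1216) = 3.44.
- 20 lost, all exposed: (20/40)/(324/1216) = 1.88.
- 5 lost in each group: (35/35)/(309/1221) = 3.95.

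So the attenuation depends on where the losses fall. Equal losses in the two groups leave the odds ratio almost unchanged.

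**6. Would restriction to infants sampled before antibiotics repair it?** Take the second case above, with all 20 treated-first exposed cases dropped, and assume that 10% of exposed non-cases (30.4) were also treated first. Then (20/40)/(273.6/1216) = 2.2, against 1.88 unrestricted and a true 4.0. Restriction selects on treatment and recovers little here.

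**The case against.** The strongest case on the other side is that the plan is mostly silent rather than wrong. Section 7.3.4 is a sample-handling list concerned largely with who is told of each result, and no sentence says that a culture taken after antibiotics is a valid negative. The second timing statement still puts the culture first unless that is unsafe, so exceptions may be few. Infants below 34 weeks, who receive antibiotics automatically, are excluded (Section 7.1.2). Designated study staff take the samples. Clinician diagnosis and GAIA level are recorded, and the logistic regression in Section 5 covers clinical as well as microbiological diagnoses, so treated culture-negative infants are not invisible.

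Much of this stands. Four stronger conclusions that a reader might infer are not supported:

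- **That the plan declares these cultures valid negatives.** It does not. Negative is the default from a list with no other place for them.
- **That cases will be hidden, or a given odds ratio reached.** The documents contain neither f nor s, nor how losses divide between exposed and unexposed infants.
- **That the CRF lacks antibiotic timing.** The Section 3 table is incomplete in the available copy between the antenatal and neonatal rows, so absence cannot be shown. Scanned records are also available for review.
- **That sampling anywhere up to 48 hours is itself a bias.** Both wordings fall inside the 72-hour definition of early onset in Section 3, and no harm from the spread is shown.

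What the objection does not remove is the conflict between the two sentences and the absence of a rule for the resulting cultures. The clinical diagnoses sit beside the culture outcome and leave its label unchanged.

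**Conclusion.** The concern holds in a limited form. The two statements in Section 5 differ on whether culture before antibiotics is mandatory and on the sampling window. Followed as written, Section 7.3.4 makes a no-growth culture after antibiotics a negative for the Phase 1 primary outcome. Section 1 gives a reason to expect such infants to be disproportionately high-risk, so the misclassification could be differential and could weaken risk-factor estimates.

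Its size is unknown. The range of 1 to 30 lost cases out of 80, and odds ratios from 3.95 down to 1.88 against a true 4.0, rest wholly on assumed inputs and show only that the effect could be trivial or material. Nothing here shows that the study is invalid. This is an inexpensive improvement, best made before the data are analysed.

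**What to change.** 1. Reconcile the two timing statements in Section 5. Which clinical rule applies is for the clinical team.
2. Make sure the CRF captures the times of birth, culture and first neonatal antibiotic, if it does not already.
3. In the outcome definition, flag a no-growth culture drawn after antibiotics as outcome unverified. Keep cultures that are positive after antibiotics as positives.
4. Add culture timing relative to antibiotics to the pilot review, and report the number of infants flagged.
5. Pre-specify sensitivity analyses of both the machine learning model and the logistic regression with flagged infants (a) counted as negative, (b) excluded, and (c) classified by the recorded clinician diagnosis or GAIA level. None of these recovers the true label; agreement across them would show that the issue does not matter in practice.
6. Do not restrict the principal model to infants sampled before antibiotics, because that selects on treatment and removes high-risk infants from the intended population.

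The cost is at most a few time fields, one classification rule and a little extra analysis. If the times are not captured prospectively, they would have to be recovered from paper notes and scans.
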